#### Definition of test positive:

A positive reference standard (FFA) test is one showing typical changes of nAMD as described above and as determined by an experienced ophthalmologist,

#### 3.4. Study population

Patients with newly diagnosed nAMD in one eye and an unaffected second eye (study eye)

Setting: Secondary care, ophthalmology outpatient departments

# 3.5. Planned inclusion and exclusion criteria

Inclusion criteria:

- Newly diagnosed nAMD in one eye and an unaffected second eye (diagnostic FFA to be within 6 weeks prior to consent)
- About to commence or recently commenced anti VEGF therapy in the first eye
- Age 50 -95

Exclusion criteria:

- patients with a history of nAMD in both eyes;
- nAMD in study eye detected at baseline;
- presenting visual acuity worse than 68 letters;
- retinal pathology in the study eye which can confound subsequent assessments (e.g diabetic retinopathy, macular hole);
- not undergoing regular monitoring in standard of care;
- patients who cannot give informed consent;
- unable to undergo a fundus fluorescein angiography (FFA) test;
- patients whose diagnostic FFA was more than 6 weeks ago

# 3.6. Recruitment and Study Procedures

# 3.6.1. Identifying participants

#### Definition of 'newly diagnosed'

For the purpose of EDNA, a patient is defined as 'newly diagnosed' if they are newly referred to secondary care and have had a diagnosis of neovascular AMD in one eye only and begin treatment with an anti VEGF. At the point of enrolment into EDNA (i.e. consent) this must be within 6 weeks of diagnosis by an FFA (the diagnostic FFA). Although a time interval of 6 weeks is permitted, it is recommended that enrolment into EDNA with appropriate data extraction occurs sooner than the maximum permitted 6 week window.

#### Patient approach

Patients newly diagnosed with nAMD will be identified by the clinician or research nurse in each centre. Patients will be approached by the clinician or research nurse at the time of diagnosis. Information about this study will be given to potentially eligible patients. A log of potentially eligible patients will be taken in order to document reasons for non-inclusion in the study to inform the study flow diagram. Patients who agree to participate will be invited to attend a study clinic. This may take place any time from the date of initial diagnosis (by diagnostic FFA) until 6 weeks later. A full baseline eligibility assessment (according to inclusion and exclusion criteria listed in section 3.5) will be undertaken at the first study visit (See flow chart). Once a patient has been confirmed as eligible, informed consent will be obtained by an appropriately trained individual.

# 3.6.2. Informed consent

Informed consent to participate in the study will be sought and obtained according to the principles of Good Clinical Practice (GCP). Informed signed consent will be obtained from the participants in all centres, by an appropriately trained individual. Participants will be given

sufficient time to accept or decline involvement and will be free to withdraw from the study at any time. Participants who cannot give informed consent (e.g. due to their mental state) will be not be eligible. The participants will be asked to consent to participation with an option to consent for the following: follow up; contact in the future about this and other research; electronic tracing using NHS data; and data linkage with routine NHS data sources; consent to the taking and storage of blood.

In order to facilitate recruitment, potentially eligible patients who have been diagnosed in clinic may also be approached about EDNA participation via telephone during this 6 week window.

# 3.6.3. Ineligible and non-recruited participants

Brief details of all screened patients will be recorded (including – where known – age and sex). Reasons for ineligibility or if eligible but declined to take part, reasons for declining will be logged whenever possible.

# **3.6.4.** Baseline measurements

The list of procedures by visit is shown in Table 1.

The diagnostic FFA is collected as part of routine care and used to assess eligibility prior to consent. This FFA measurement is used as the baseline FFA for EDNA and therefore does not need to be repeated after consent. Any EDNA diagnostic tests (described in section 3.2 above) which have already been collected as part of routine care within 6 weeks prior to consent may be included in the case report form for the baseline measurement.

The following assessments may be performed at the baseline study visit if data from the routine visit is not available in order to establish a baseline for all the index tests at study entry. VA in the EDNA study eye. Recording of findings arising from slit lamp biomicroscopy with particular emphasis on the status of the macula and the vitreo retinal interface. Colour fundus photography central macular fields 1 and 2 and a single wide field image if appropriate equipment is available. Fundus autofluorescence with blue or green (optional). Macular raster OCT without and with enhanced depth imaging of the choroid. Amsler chart completion.

Patients who consent to have blood collection and storage will have blood collected at baseline and at study exit.

A participant will enter the EDNA cohort if measurements on the baseline case report form have fulfilled the eligibility criteria, and informed consent and all baseline measurements have been obtained within 6 weeks of diagnostic FFA.

# **3.6.5.** Blood collection and storage

Patients who agree to the collection of blood will have approximately 20ml of blood collected at their study visit. Blood will be labelled with a code and any personal details will be removed. The coding will maintain confidentiality whilst allowing biological details to be analysed. The samples collected in this study will be sent to Queen's University Belfast for storage and will be stored indefinitely. Research using the samples will be conducted only after approval by a Research Ethics Committee. Participants may grant advance authorisation for possible future research, with the understanding that confidentiality will be fully protected or can consent just for the analysis for the needs of the EDNA study.

#### 3.6.6. Follow-up procedures

Once enrolled into the study, the participants will be clinically monitored following standard clinical practice in the eye with nAMD. The standard of care in the NHS for patients newly diagnosed with nAMD is regular (approximately every 8 weeks) assessment and treatment as required. At each follow up clinic visit VA, clinical signs on fundus, comments on the OCT appearance, self reported function and Amsler [index tests that are performed in the EDNA study eye] will be extracted. A FFA (reference standard assessment) will be triggered if any of the index tests are positive (see flow chart). Following this a clinical diagnosis of the presence of nAMD in the study eye will be made. If nAMD is diagnosed the patient will be clinically monitored and treated as per local clinical practice.

At M 18 a study visit which will occur if the participant remains in the study by virtue of not having experienced a neovascular event in the EDNA study eye, all tests undertaken at baseline along with an FFA will be performed with subsequent clinical diagnosis of the presence of nAMD in the study eye. Similarly, at M 36 a study exit visit which will occur if the participant remains in the study by virtue of not having experienced a neovascular event in the EDNA study eye during the entire period of follow up, all the tests recorded at baseline along with an FFA will be performed.

If, as part of routine clinical management, an additional FFA is performed in the non study eye and results in the detection of nAMD in the EDNA study eye then these results should be recorded in the EDNA CRF and study monitoring follow-up will cease.

# 3.6.7. End of participant follow-up

All patients will be followed-up according to standard clinical practice up to 3 years from enrolment. Study monitoring follow-up will end prior to 3 years upon a clinical diagnosis of nAMD in the study eye or if a patient withdraws consent to continue this follow-up (see section 3.6.8 for information on the withdrawal procedures).

# 3.6.8. Change of Status/Withdrawal procedures

Participants will remain in the study unless they choose to withdraw consent or if they are unable to continue for a clinical reason. All changes in status with the exception of complete withdrawal of consent will mean the participant is still followed up for all study outcomes wherever possible. All data collected up to the point of complete withdrawal will be retained and used in the analysis unless the participant requests this to be destroyed and excluded. If the participant had previously consented to and donated blood for storage, and the participant later withdraws consent, they may also request for their donated blood to be destroyed.

# 3.6.9. Subsequent arrangements

# Informing key people

Following formal study entry the local research officer will:

- 1) Inform the participant's General Practitioner (by letter enclosing information about the EDNA study and Study office contact details).
- 2) File the hospital copy of the consent form in the hospital notes along with information about the EDNA study.
- 3) Use the EDNA study database to enter data regarding the participant

4) File study documentation according to local regulations.

# Notification of/by GPs

GPs are asked to contact the study office if one of the participants moves, becomes too ill to continue or dies, or any other notifiable event or possible serious adverse event occurs. Alternatively, staff at the study office may contact the GP.

#### 4. SAFETY

#### 4.1. Definitions

Within the EDNA study we will record only any AE/SAE relating to collection of blood or FFA requested during involvement in the study. AEs relating to FFAs conducted prior to recruitment to the study will not be reported.

Any AE/SAE resulting from treatment to the nAMD eye during the study will not be recorded as an AE/SAE. Once an EDNA participant has nAMD in the study eye, or the end of follow-up, any subsequent AE or SAE will not be recorded.

An **adverse event** (AE) is any untoward medical event affecting a clinical study participant. Each initial AE will be considered for severity, causality or expectedness and may be reclassified as a serious event or reaction based on prevailing circumstances.

A serious adverse event (SAE), is any AE, that:

- results in death;
- is life threatening (i.e. the subject was at risk of death at the time of the event; it does not refer to an event which hypothetically might have caused death if it were more severe);
- requires hospitalisation or prolongation of existing hospitalisation;
- results in persistent or significant disability or incapacity;
- is a congenital anomaly or birth defect,
- is otherwise considered medically significant by the investigator

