# 4.2. Procedures for detecting, recording, evaluating & reporting AEs, SAEs

# 4.2.1. Detecting AEs and SAEs

All AEs and SAEs as defined in section 4.1 above must be recorded from the time a participant consents to join the study until the last study visit.

The Investigator should ask about the occurrence of AEs/SAEs at the next study visit after any study FFA or blood collection. If there is any doubt as to whether a clinical observation is an AE, the event should be recorded.

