# 4.2.2. Recording AEs and SAEs

Depending on severity, when an AE/SAE occurs after blood collection or FFA, it is the responsibility of the Investigator (or delegate) to review appropriate documentation (e.g. hospital notes, laboratory and diagnostic reports) related to the event. The Investigator (or delegate) should then record all relevant information in the CRF and on the SAE form if it is an SAE.

Information to be collected includes type of event, onset date, Investigator assessment of severity and causality, date of resolution as well as treatment required, investigations needed and outcome.

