### **Safety data**

Within the EDNA study we will record only any AE/SAE relating to collection of blood or FFA requested during involvement in the study. AEs relating to FFAs conducted prior to recruitment to the study will not be reported.

Any AE/SAE resulting from treatment to the nAMD eye during the study will not be recorded as an AE/SAE. Once an EDNA participant has nAMD in the study eye, or the end of follow-up, any subsequent AE or SAE will not be recorded.

In this study the only AE and SAE that are expected relate to the collection of blood and the FFA.

FFA related expected adverse events: These may be local skin irritation, development of erythematous lesions on the skin immediately after FFA and more generalised reaction to the FFA with pulmonary and or other systemic manifestations (anaphylaxis)

Blood collection expected adverse events: bruising and discomfort at the site of any puncture.

Most participants in the study will be elderly, and we anticipate that 50% will be >75 years at the time of recruitment. Therefore it is expected that a proportion of the cohort will die from causes unrelated to the study over the period of follow up. Deaths unrelated to the study procedures will not be recorded as SAEs but will be recorded within the CRF.

## Appendix 1

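### Adverse-event recording stops at nAMD diagnosis or end of follow-up with no exception for the study's own last FFA and blood draw, so delayed reactions to them are excluded as written

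*Protocol*

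**What the plan says.** Safety scope is narrow by design. In the words of the SAP (Safety data), which match Protocol 4.1, "we will record only any AE/SAE relating to collection of blood or FFA requested during involvement in the study". Both documents then set a stopping rule: "Once an EDNA participant has nAMD in the study eye, or the end of follow-up, any subsequent AE or SAE will not be recorded". Neither makes an exception for an event caused by a study FFA or a study blood draw.

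Protocol 4.2.1 words the window differently: events "must be recorded from the time a participant consents to join the study until the last study visit". It schedules one enquiry: "The Investigator should ask about the occurrence of AEs/SAEs at the next study visit after any study FFA or blood collection". It adds that "If there is any doubt as to whether a clinical observation is an AE, the event should be recorded".

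Protocol 4.2.2 sets no end date: "when an AE/SAE occurs after blood collection or FFA, it is the responsibility of the Investigator (or delegate) to review appropriate documentation", and then to record the event.

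On the procedures themselves, Protocol 3.6.4 says that consenting patients "will have blood collected at baseline and at study exit". Table 1 in both documents ticks blood collection in the column for a positive FFA and again in the final column (3 years in the protocol, exit in the SAP). Protocol section 3 and 3.6.6 place FFAs at 18 months and 3 years for participants who have not converted, besides any triggered FFA.

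**The concern.** FFA and blood collection are the only procedures whose harms the study sets out to capture. The stopping rule takes effect at the moment when the last of each is done. A participant who reacts a day after the confirming FFA, or after the exit visit, has no later study visit at which the question is due. If the event becomes known anyway, 4.1 tells the site not to record it, while 4.2.2 tells the site to record it.

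What is at stake is the completeness of the safety record. Protocol 4.2.4 promises notification of the sponsor and the ethics committee for serious, related and unexpected events, and summaries of all related SAEs in progress reports. An event that is never entered cannot reach that chain. Sensitivity, specificity, the economic model and the risk model do not depend on it.

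**Working it through.** The plan states no figure for adverse events, so there is none to reproduce. The check is a comparison of the rules, followed by a count of procedures for scale.

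**Step 1. Where the cut-off falls.**
- Converters: the FFA is done first and the clinical diagnosis follows it (Protocol 3.6.6). Study monitoring ends on diagnosis (3.6.7). Table 1 places a blood draw after the positive FFA.
- Non-converters: the last FFA and the last draw both belong to the 3-year exit visit (3.6.4, 3.6.6, Table 1). Section 16 defines end of follow-up as the last data capture, which is in effect that visit.

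No later study visit, call or safety window is described in either case.

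**Step 2. The same event under each rule.**

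| Event | 4.1 and SAP | 4.2.1 window | Enquiry due under 4.2.1 | 4.2.2 |
|---|---|---|---|---|
| Reaction during the confirming FFA, before diagnosis | Recordable | Inside | Seen at the visit | Record |
| Delayed reaction to the confirming FFA | Barred | Outside, if that was the last study visit | None scheduled | Record |
| Converter's draw after a positive FFA, immediate event | Barred on a literal reading | Inside, if at the same visit | Seen at the visit | Record |
| Converter's draw, delayed event | Barred | Outside | None scheduled | Record |
| Reaction at the exit visit, FFA or draw | Recordable | Inside | Seen at the visit | Record |
| Delayed reaction after the exit visit | Barred | Outside | None scheduled | Record |

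The three protocol sections agree on acute reactions to the FFA and on reactions at the exit visit. They disagree in the other four rows.

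**Step 3. Other routes.** Protocol 3.6.9 asks GPs to tell the study office if "any other notifiable event or possible serious adverse event occurs". That may bring an event to light, but 4.1 still bars recording it after the cut-off. The documents do not define whether a routine clinic visit after conversion counts as a study visit. If it does, the question could be asked, and 4.1 would again bar the answer. The SAP repeats the rule and so does not repair it.

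**Step 4. Scale, in procedures and not in events.** Inputs: 560 participants (Protocol 7.2) and 28% cumulative conversion at 3 years (7.1).
- Converters: 560 × 0.28 = 156.8, about 157 confirming FFAs.
- Non-converters: 560 × 0.72 = 403.2, about 403 exit FFAs due, before losses.
- Assume each non-converter has only the 18-month and 3-year FFAs, and each converter has one or two post-baseline FFAs. The documents give no number of negative triggered FFAs, so none is counted.
- One FFA per converter: 560 / (2 × 403.2 + 156.8) = 560 / 963.2 = 58%.
- Two FFAs per converter: 560 / (2 × 403.2 + 2 × 156.8) = 560 / 1120 = 50%.

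Every negative triggered FFA lowers this share. For those who consent to blood collection, the final draw is one of two planned draws.

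**The case against.** The strongest reply is that the stopping sentence directly follows the exclusion of events from treatment of the nAMD eye. It can be read as leaving out events from care after conversion, and not reactions to the confirming FFA. On that reading 4.2.2 and the record-if-in-doubt instruction govern. The only FFA reaction whose timing is described (4.1, expected events) is a skin reaction straight after the test. The study has no interventional aspect, safety is not an outcome, and the SAP's adverse-event tables are listings without rates or denominators.

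Much of this stands, and it limits the point. Four stronger readings that a reader might infer are not supported:

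- *All events from every participant's last FFA and exit draw are lost.* The FFA precedes the diagnosis and exit procedures happen at the exit visit, so acute reactions there are inside the rule. Blood collection is optional. A participant whose last FFA was negative and who attended again before leaving could be asked.
- *Events are sought only at the next study visit.* Protocol 4.2.1 says that the investigator should ask then. It does not say that this is the only route, and 4.2.2 and the GP route exist.
- *Adverse-event rates will be understated and a serious reaction would go unreported.* No rate is planned, and the documents give no frequency of delayed events. Anaphylaxis is listed as expected, so the route for unexpected events would not apply to it in any case.
- *Taking 12% off 560 gives the number who reach a final FFA.* The 12% in Protocol 7.1 covers indeterminate and missing results as well as loss to follow-up, so it is not an attrition rate.

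What does not stand is the claim that the text is already clear. The stopping sentence refers to any subsequent event and makes no exception, and a site cannot follow both 4.1 and 4.2.2 for a delayed reaction to a confirming FFA.

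**Conclusion.** The point holds in a limited form. Delayed events after the confirming or 3-year exit FFA, and after the final draw in those who consented to it, have no scheduled enquiry and are excluded by the literal text of Protocol 4.1 and the SAP. In converters the literal exclusion reaches even immediate events from the draw that Table 1 places after a positive FFA. Protocol 4.1, 4.2.1 and 4.2.2 state three different windows.

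The gap concerns the last study FFA of up to about 157 converters and 403 non-converters, which is 50% to 58% of post-baseline FFAs under the assumptions shown. That is a share of procedures. The number of events missed cannot be derived from the documents and may be small. The conclusion takes having nAMD in 4.1 to mean having been diagnosed with it, and takes no study visit to follow diagnosis or exit. The consequence is confined to safety reporting.

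**What to change.** Reconcile Protocol 4.1, 4.2.1, 4.2.2 and the SAP safety text. State that AEs and SAEs attributable to a study FFA or study blood draw are recorded whatever the nAMD status, within a stated window after the procedure. The exclusion of events from treatment of the nAMD eye can stay as it is.

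Ascertain these events with one question at the next routine clinic contact. For converters, an added item in the planned post-conversion case-note review would also serve. That review does not cover non-converters, so for them the amended text should name the clinic contact and say what happens when there is none within the window.

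The cost is a minor wording amendment, one extra question or extraction item, and slightly more recorded events. No accuracy analysis changes.

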#### EDNA Expected adverse events:

In this study the only AE and SAE that are expected relate to the collection of blood and the FFA.

FFA related expected adverse events: These may be local skin irritation, development of erythematous lesions on the skin immediately after FFA and more generalised reaction to the FFA with pulmonary and or other systemic manifestations (anaphylaxis)

Blood collection expected adverse events: bruising and discomfort at the site of any puncture

#### **Reporting of deaths during the study:**

Most participants in the study will be elderly, and we anticipate that 50% will be >75 years at the time of recruitment. Therefore it is expected that a proportion of the cohort will die from causes unrelated to the study over the period of follow up. Deaths unrelated to the study procedures will not be recorded as SAEs but will be recorded within the CRF.

# 4.2. Procedures for detecting, recording, evaluating & reporting AEs, SAEs

# 4.2.1. Detecting AEs and SAEs

All AEs and SAEs as defined in section 4.1 above must be recorded from the time a participant consents to join the study until the last study visit.

The Investigator should ask about the occurrence of AEs/SAEs at the next study visit after any study FFA or blood collection. If there is any doubt as to whether a clinical observation is an AE, the event should be recorded.

# 4.2.2. Recording AEs and SAEs

Depending on severity, when an AE/SAE occurs after blood collection or FFA, it is the responsibility of the Investigator (or delegate) to review appropriate documentation (e.g. hospital notes, laboratory and diagnostic reports) related to the event. The Investigator (or delegate) should then record all relevant information in the CRF and on the SAE form if it is an SAE.

Information to be collected includes type of event, onset date, Investigator assessment of severity and causality, date of resolution as well as treatment required, investigations needed and outcome.

